1.4 STUDY PLAN

The following study flow chart and figure describes the design of the study:

STUDY FLOW CHART

	Screening and training			Treatment Period (15-16 weeks)																Follow up	
	1	2*	3	4 ^a ☐	5 ^a ☐	6 ^a ☐	7	8 ^a ☐	9 ^a ☐	10 ^a ☐	11	12 ^a ☐	13 ^a ☐	14 ^a ☐	15	16 ^a ☐	17 ^a ☐	18 ^b	19	20 ^a ☐	
Visit Windows: Visit 4 - 19: ± 3 days																					
Week	-4	-3-1	(R)	1	2	3	4	5	6	7	8	9	10	11	12	13	14	15	16	2+2 days	
Informed consent	X																				
Inclusion/Exclusion criteria	X	X	X																		
Medical and surgical history; diabetes history	X																				
Physical examination, including neuropathy screening	X																				
Vital signs ^c and Body weight	X		X				X				X				X					X	
Height	X																				
Dispensation/collection of study diary	X	X	X				X				X				X			X	X		
Dispensation of study medication			X				X				X				X						
IMP compliance Check; collecting and counting used and unused pens							X				X				X			X	X		
IVRS call	X		X				X				X				X					X	
Randomization			X																		
Documentation and review of basal and bolus insulin dose	X	X	X	X	X	X	X	X	X	X	X	X	X	X	X	X	X	X	X		
Change from BID to QD basal insulin injection (if applicable)		X																			
CGM, SMPG:																					
Training and re-training: Glucometer, SMPG profiles, study diary	X	X	X				X				X				X			X			
Dispensation glucometer,	X																				
Dispensation CGM device; Blinded CGM ^d		X																X			
Upload CGM to PC			X																	X	
Collect CGM device			X																	X	
SMPG ^e	X	X	X	X	X	X	X	X	X	X	X	X	X	X	X	X	X	X	X	X	X
Upload SMPG to PC		X	X				X				X				X			X	X		
Concomitant medication	X	X	X	X	X	X	X	X	X	X	X	X	X	X	X	X	X	X	X	X	X
Central Laboratory																					
HbA1c, Fasting plasma glucose (FPG)	X										X									X	

Visit Windows: Visit 4 - 19: ± 3 days	Screening and training			Treatment Period (15-16 weeks)																Follow up
	1	2 ^a	3	4 ^a ☐	5 ^a ☐	6 ^a ☐	7	8 ^a ☐	9 ^a ☐	10 ^a ☐	11	12 ^a ☐	13 ^a ☐	14 ^a ☐	15	16 ^a ☐	17 ^a ☐	18 ^b	19	20 ^a ☐
Week	-4	-3 -1	(R)	1	2	3	4	5	6	7	8	9	10	11	12	13	14	15	16	2+2 days
C-peptide ^f	X																			
Safety Laboratory																				
Hematology ^g , Clinical Chemistry ^h	X																			
Urine analysis ⁱ	X																			
Pregnancy test (WOCBP only) ^j	X		X				X				X				X				X	
AE / SAE	To be assessed and reported (if any) throughout the study (report SAE to the sponsor within 24 hours)																			

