1.6 STATISTICAL MODIFICATIONS MADE IN THE STATISTICAL ANALYSIS PLAN

Three statistical modifications were made in the statistical analysis plan.

- 1) Per protocol, during Week 15, patients will wear a blinded CGM device for 7 consecutive days to generate a minimum 4 days of useable CGM data. If a patient fails the first attempt for any reason, he/she will be retrained for CGM conduct and complete another course of blinded CGM in Week 16. If the patients fails the first week of CGM, only the second week CGM data will be used for data analysis and determine whether there are sufficient data to derive CGM variables. A statistical modification was made that if the second week CGM data are not sufficient per steps 1-6 above either and two weeks pooled together can generate a minimum 4 days of usable CGM data, then CGM data from both weeks will be pooled together to derive CGM variables.

- 2) An additional secondary endpoint, the mean change of each participant's glucose level during the last four hours of CGM data collection prior to next day's basal insulin injection, was added.
- 3) If there are more than hypoglycemia events within 30 minutes interval, the one with the lowest glucose level will be used.

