2.4.4 Analyses of efficacy endpoints

2.4.4.1 Analysis of primary efficacy endpoint(s)

The percentage of time glucose in target range 70-180mg/dL (3.9–10mmol/l) during week 16 (obtained from CGM) will be calculated based from the denominator of total time with valid data. The criteria to evaluate baseline and Week 16 CGM data are in Section 2.1.3.

The evaluable assessment interval for the calculation will comprise of 24-hour periods during Week 16 for which there is sufficient non-missing data. In order to be evaluable for analysis, a patient needs at least 4 days of 24-hour data meeting this criterion and should not receive protocol prohibited medication.

The endpoint will be summarized by treatment group using mean, median, standard deviation, minimum and maximum.

Differences between treatment groups will be assessed using a generalized linear model with identity link, adjusting for key baseline characteristics (duration of diabetes, baseline BMI, age and baseline value) and randomization strata if model permits. If model does not converge, for example due to over 90% patients fall into the carbohydrate counting, the specific factors which cause non convergence may be dropped from the model. Adjusted mean estimates for each treatment group with standard errors, the adjusted estimate of treatment mean difference with standard error and a 95 % confidence interval for the treatment mean difference will be provided. The statistical test will be for superiority of Toujeo over Lantus, two-sided and at a 5% significance level.

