2.4.4.2 Analyses of secondary efficacy endpoints

The main secondary efficacy endpoints.

The seven main secondary efficacy endpoints will be analyzed as below and tested sequentially after the primary endpoint. Testing strategy is described in 2.4.4.3

The incidence (proportion of patients with any nocturnal symptomatic hypoglycemia events) will be analyzed using logistic regression, adjusting for randomization strata and other baseline characteristics (duration of diabetes, baseline BMI and age) if the model permits.

The risk ratio (RR) of hypoglycemia of Toujeo versus Lantus will be assessed by a log-binomial regression model adjusting for randomization strata and other baseline characteristics (duration of diabetes, baseline BMI and age) if the model permits.

The rate (number of events per patient-year) of nocturnal symptomatic hypoglycemic events will be analyzed using an over-dispersed Poisson regression model, adjusting for randomization strata and other baseline characteristics (duration of diabetes, baseline BMI and age) if the model permits.

The mean change of each participant's glucose level during the last four hours of CGM data collection prior to next day basal insulin injection comparing Toujeo versus Lantus will be analyzed using a mixed model, in which treatment arm is a fixed categorical effect and patient is a random effect, adjusting for randomization strata and other baseline characteristics (duration of diabetes, baseline BMI and age) if the model permits. If a patient has more than 7 evaluable days of CGM data, only the first 7 days closest to Week 15 will be included.

The percentage of time glucose concentrations obtained by CGM within the target range of 70-140 mg/dL (3.9-7.8 mmol/L) during the last 4 hours of CGM data prior to the next day basal insulin injection will be summarized and analyzed by the same model as the primary endpoint.

Total, within day and between day standard deviation (SD) will also be summarized and analyzed by the same model as the primary efficacy endpoint.

Other endpoints

The total, within day and between day CV% and SD will be summarized at baseline and study endpoint by treatment group using mean, median, standard deviation, minimum and maximum, and will be analyzed as for the primary endpoint.

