The incidence and rate (nocturnal or 24 hours) of all hypoglycemic events will be analyzed for the hypoglycemia categories of severe, documented symptomatic, asymptomatic, probable and relative, as defined in the publication of the ADA Workgroup on Hypoglycemia, 2015. These hypoglycemia categories will be analyzed as for nocturnal symptomatic hypoglycemia described previously.

The percentage of time plasma glucose in target range 70-140 mg/dL (3.9–7.8 mmol/L), the percentage of time plasma glucose <70 mg/dL (3.9 mmol/L), <54 mg/dL (3 mmol/L), the percentage of time glucose >140 mg/dL (7.8 mmol/L), >180 mg/dL (10 mmol/L) and > 250 mg/dL (13.9 mmol/l) will be calculated and summarized and analyzed as for the primary endpoint. For these endpoints, the time period of observation will be all evaluable time (24 hours) and nocturnal, where nocturnal is defined as the period between 00:00-05:59 within the evaluable assessment interval.

All other continuous CGM endpoints including the glucose variability parameters (MAGE, DT, AUC, CONGA-1, CONGA-2, CONGA-4) will be summarized, and will be analyzed using the same model as described for the primary endpoint.

The absolute values, each post-prandial to pre-prandial excursion and change in 7-point SMPG profiles (pre-prandial and 2-hour post-prandial plasma glucose at breakfast, lunch and dinner, and bedtime) from baseline to Week 12, Week 16 and the last on-treatment value (study endpoint) will be presented descriptively by treatment group.

Summary statistics will also be presented for the absolute values and the change from baseline in HbA1c and central lab FPG to Week 8, Week 16 and last on-treatment value (study endpoint). The change from baseline to study endpoint will be analyzed using a mixed-effect model with repeated

measures (MMRM) approach under the missing at random framework, using an adequate contrast at endpoint. The model will include fixed categorical effects of treatment arm, visit, treatment-by-visit interaction, randomization strata, and baseline HbA1c as covariate as well as baseline HbA1c-by-visit interaction.

Median, the first and the third quartiles and 10% and 90% percentiles of the curves, which are used to calculate the primary endpoint and secondary CGM endpoints, will be plotted for each treatment group.

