2.5.3 Missing data

For categorical variables, patients with missing data are not included in calculations of percentages unless otherwise specified. When relevant, the number of patients with missing data is presented.

Handling of CGM measurements outside detection range

CGM blood glucose values below the lower limit and above upper limit of detection range will be set to the lower and upper limits of detection, respectively, for the CGM parameter derivation.

Handling of computation of treatment duration if investigational medicinal product end of treatment date is missing

For the calculation of the treatment duration, the date of the last dose of IMP is equal to the date of last administration reported on the end-of-treatment case report form page. If this date is missing, the exposure duration should be left as missing.

The last dose intake should be clearly identified in the case report form and should not be approximated by the last returned package date.

Handling of missing baseline and end of treatment IMP doses

For baseline and end of treatment IMP dose calculations, if the dose on the date of randomization or the dose at the end of treatment is not available, the last available dose within 2 days prior to randomization and the last available dose within 2 days prior to the end of the treatment will be used.

Handling of missing IMP injection time for the purpose of CGM parameter calculation

For the calculation of secondary efficacy end point, percentage time glucose concentrations obtained by CGM within target range of 70-140 mg/dL (3.9–7.8 mmol/L) during the last 4 hours of CGM data collection prior to next day basal insulin injection, if the injection time of the IMP is missing, the injection time from the prior day will be used as it is assumed that IMP should be injected at the same time in the morning.

Handling of medication missing/partial dates

No imputation of medication start/end dates or times will be performed. If a medication date or time is missing or partially missing and it cannot be determined whether it was taken prior or concomitantly, it will be considered a prior, concomitant, and posttreatment medication.

Handling partial date of birth:

For calculation age, missing birth day is assumed as the 15 of the month. If month is missing, the age will be calculated as Year of date of consent- Year of birth.

Handling of partial date of diagnosis of Type 1 diabetes

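### The third hierarchical secondary test (glucose change over the last four hours before injection) and the FPG change model omit the endpoint's own baseline; the cost is precision, possibly very little for the former

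*SAP*

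**What the plan says.** **Third secondary test.** SAP 1.6 adds to the protocol's endpoints "the mean change of each participant's glucose level during the last four hours of CGM data collection prior to next day's basal insulin injection". SAP 2.4.4.3 places it third of seven secondary tests. SAP 2.4.4.2 fits a mixed model with treatment fixed, and "patient is a random effect, adjusting for randomization strata and other baseline characteristics (duration of diabetes, baseline BMI and age) if the model permits". At most seven evaluable days per patient enter.

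**Fourth secondary test, same window.** Percentage of time at 70–140 mg/dL over the last four hours "prior to the next day basal insulin injection will be summarized and analyzed by the same model as the primary endpoint". That model (SAP 2.4.4.1) is fitted "adjusting for key baseline characteristics (duration of diabetes, baseline BMI, age and baseline value) and randomization strata if model permits". The remaining continuous CGM endpoints likewise "will be summarized, and will be analyzed using the same model as described for the primary endpoint".

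**HbA1c and FPG.** SAP 2.4.4.2 gives one MMRM for both changes. Apart from treatment, visit and their interaction, its terms are "randomization strata, and baseline HbA1c as covariate as well as baseline HbA1c-by-visit interaction". The protocol synopsis and Protocol 11.4.2.2 say the same. The flow charts schedule central-laboratory HbA1c and FPG together at Visit 1, so a baseline FPG exists.

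**Testing order.** Under SAP 2.4.4.3 each hierarchical conclusion needs the preceding test to be significant. Endpoints outside the sequence, FPG among them, have nominal p-values only.

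**The concern.** A patient's own baseline is usually among the most useful covariates for a continuous outcome. The plan uses it for the primary endpoint, for the fourth test and for the other continuous CGM variables, but not for the third test. The covariate list there matches the one used for the hypoglycemia models just above it, and no reason is given. For FPG, the shared sentence read literally conditions on a different variable's baseline.

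At stake is efficiency. The third test counts only if the primary and the two hypoglycemia tests succeed. It then controls access to tests four to seven, so a miss caused by avoidable noise would also close those. For FPG the stake is a wider interval around a descriptive result.

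**Working it through.** **1. The plan's own figure.** SAP 1.3: difference 4, SD 14, two-sided 5%, 90% power. n = 2(1.960 + 1.282)² × 14²/4² = 257.4, so 258 per arm (259 with the exact t). At the stated 262 the power is 0.905 (0.904 by t), and 308 × 0.85 = 261.8. The stated figure reproduces. It concerns the primary endpoint; the documents give no SD, correlation or power for the third test or for FPG, so everything below rests on assumed correlations.

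**2. Third test, change within the window.** With similar numbers of days per patient, the mixed model in effect compares patient means. Let ρ be the correlation between a patient's baseline and endpoint means, given the covariates already in the model. Adding the baseline multiplies the variance of the treatment difference by 1 − ρ². A test with 80% power then has power Φ[(1.960 + 0.842)/√(1 − ρ²) − 1.960].

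| ρ | Variance cut | SE ratio | Power, from 80% |
|---|---|---|---|
| 0 | 0% | 1.000 | 80.0% |
| 0.1 | 1% | 0.995 | 80.4% |
| 0.2 | 4% | 0.980 | 81.6% |
| 0.3 | 9% | 0.954 | 83.6% |
| 0.5 | 25% | 0.866 | 89.9% |

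**3. Which ρ?** With m days in each period, day-to-day intraclass correlation ICC, and stability s of the true patient means, ρ = s × m·ICC/[1 + (m − 1)·ICC]. For m = 4–7 and s = 0.5–0.9:
- ICC 0.05–0.10 gives ρ of about 0.09–0.39, a variance cut of 1–16%.
- ICC 0.3 gives a cut of 10–46%.

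Fewer baseline days reduce the gain. Take ICC 0.2, s 0.75 and six endpoint days. With three baseline days, ρ² = 0.15²/[(0.2 + 0.8/3)(0.2 + 0.8/6)] = 14.5%; with six it is 20.2%.

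**4. Validity.** In a simulation with 262 patients per arm, 4,000 trials per setting and no selective loss, type I error was 4.7–5.0% with or without the covariate, and no bias was visible. Power without and with it was 79.9% and 82.4% at ρ = 0.25, and 80.5% and 90.3% at ρ = 0.5. This agrees with the formula.

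**5. FPG change, baseline FPG in place of baseline HbA1c.** Take one visit with unit variances. Let r be the correlation of baseline with endpoint FPG, and b0 and b1 the correlations of baseline HbA1c with baseline and endpoint FPG. The residual variance of the change is 2(1 − r) − (b1 − b0)² given HbA1c and 1 − r² given FPG. With b0 = 0.3–0.5 and b1 = 0.1–0.3, (b1 − b0)² runs from 0 to 0.16:

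| r | Given HbA1c | Given FPG | Variance cut |
|---|---|---|---|
| 0.2 | 1.44–1.60 | 0.96 | 33–40% |
| 0.3 | 1.24–1.40 | 0.91 | 27–35% |
| 0.4 | 1.04–1.20 | 0.84 | 19–30% |
| 0.5 | 0.84–1.00 | 0.75 | 11–25% |

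Since 2(1 − r) − (1 − r²) = (1 − r)², the exchange gains whenever 1 − r exceeds |b1 − b0|, which holds throughout this range.

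**The case against.** **The unadjusted analysis is valid.** A randomized comparison does not need the baseline covariate, and for the third test the gain may be nil. Patients may move their injection time, or go from twice- to once-daily basal insulin, during screening (Protocol 8.2.3.1 and 10.1.1.2), which weakens the link between baseline and endpoint. This stands, and it limits the point to precision.

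**The gain is conditional.** It arises only after the primary and two hypoglycemia tests succeed. The plan states power for the primary and for the hypoglycemia rate (90% and 80%) but none for incidence, which is tested first of the seven. Multiplying 0.90 by 0.80 would leave incidence out, so no unconditional gain is claimed here.

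**Stronger readings that a reader might infer.**
- *The omission biases the test.* That would need evaluability to depend on baseline differently in the two arms. The efficacy set does require evaluable endpoint CGM (SAP 2.3.1.1) and about 15% loss is planned, but nothing in the documents points to such a difference.
- *The endpoint is a change from baseline, so the loss is larger.* The wording places the change inside the four-hour window. For HbA1c and FPG the SAP says explicitly when it means change from baseline, and a patient random effect with up to seven days fits one value per day.
- *The endpoint is undefined.* The SAP prints no formula, but SAP 2.1.3.2 attaches reference 1, a published CGM comparison of the two insulins, to this endpoint. The definition may be there. The missing-injection-time rule in SAP 2.5.3, whose text names only the percent-time endpoint, is likewise separate detail and adds no weight here.

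**FPG may be shorthand.** The synopsis wording suggests a sentence written for HbA1c and extended to FPG, with the respective baseline intended. That is plausible, but it is not what the text says.

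**Conclusion.** Both omissions are in the text and the point holds as a minor one. Under ignorable missingness neither biases the comparison or disturbs the type I error; the cost is precision.

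For the third test, on the natural within-window reading, the avoidable variance is 1–9% at ρ = 0.1–0.3 and 25% at 0.5, and it may be close to zero. It matters for the sequence only once that test is reached. For FPG change the loss is larger in proportion, about 11–40% for r between 0.2 and 0.5, but it touches only a nominal p-value and its interval.

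All these sizes rest on assumed correlations. The FPG figures also use a single-visit approximation that ignores the HbA1c stratum and the other terms. The documents do not support a claim that a confirmatory conclusion is unsound.

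**What to change.** **Third test (SAP 2.4.4.2).** Add as a covariate the patient's mean last-four-hour within-window change from the baseline CGM (Visit 2 to Visit 3), computed by the same definition as the endpoint, taken from reference 1. Keep patients without a usable baseline window, for example by filling in the overall baseline mean and adding a missing indicator. If a share f lacks a window, this keeps a variance cut of (1 − f)ρ². Dropping those patients instead gives a variance ratio of (1 − ρ²)/(1 − f), which cancels the gain at f = ρ²: 4% at ρ = 0.2 and 9% at 0.3.

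The cost is one derived variable and one sentence. Randomization already requires four usable baseline CGM days (Protocol 7.2.4), and the fourth test needs a baseline value from the same window under the primary model. Injection times are in the diary. The eCRF holds them for only three days before randomization (Protocol 10.2.3.2, Table 5), so using more days would need extra data entry.

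**FPG (SAP 2.4.4.2).** Use baseline FPG and baseline FPG-by-visit in the FPG model, and keep baseline HbA1c and its visit interaction for the HbA1c model. No new data are needed. Because the protocol carries the same sentence, record the departure in SAP 1.5 or 1.6. Both changes should be made before database lock.

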2.4.4.3 Multiplicity issues

Results of the secondary analyses are considered as informative only if the primary analysis is positive, and will be examined in a hierarchical step-down manner. The primary efficacy endpoint, the percentage of time glucose in target range 70-180mg/dL (3.9–10 mmol/l) during Week 16, will be tested first, followed by (1) incidence of nocturnal symptomatic hypoglycemia, (2) rate of nocturnal symptomatic hypoglycemia, (3) mean change of each participant's glucose level during the last four hours of CGM (4) percentage (%) of time glucose concentrations obtained by CGM within target range of 70-140 mg/dL (3.9–7.8 mmol/L) during the last 4 hours of CGM data collection prior to next day basal insulin injection, (5) total CV%, (6) within day CV% and (7) between day CV% . Each test was planned to be performed at 5% significance level. Inferential conclusions about these successive efficacy endpoints will require statistical significance of the previous one.

For other secondary and exploratory endpoints, nominal p-values will be presented for information only.

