11.1 DETERMINATION OF SAMPLE SIZE

A sample size of 262 evaluable patients per treatment arm would provide at least 90% power to demonstrate superiority of Toujeo over Lantus for the primary efficacy variable of the percentage of time plasma glucose within the range of 70-180 mg/dL during Weeks 15-16 of the study. The calculations were based on a superiority hypothesis using a t-test at a 2-sided 5% significance level and assumes an absolute difference of at least 4% of time in range, a common standard deviation of 14% (assumed based on the prior AM data from the PDY12777 study), and an expected value of 53% in the Lantus arm. As a generalized linear model will be used for the primary analysis, the power should be somewhat higher due to reduced estimate variability versus the t-test.

Considering prior data from the AM arms of the PDY12777 and EDITION-4 studies, this sample size would also provide at least 80% power to demonstrate a difference in the key secondary endpoint of the rate of documented symptomatic nocturnal hypoglycemia occurring at any point post randomization, assuming a rate ratio (Toujeo over Lantus) of at most 0.86 events per pt-year. Testing of this key secondary endpoint will be considered informative if superiority of the primary endpoint is met.

Calculations were made using nQuery Advisor v6.01.

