11.4.2.3 Multiplicity considerations

Results of the secondary analyses are considered as informative only if the primary analysis is positive, and will be examined in a hierarchical step-down manner. Therefore the study overall type I error does not need to be adjusted for multiplicity.

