1.3 DETERMINATION OF SAMPLE SIZE

A sample size of 262 evaluable patients per treatment arm would provide at least 90% power to demonstrate superiority of Toujeo over Lantus for the primary efficacy variable of the percentage of time plasma glucose within the range of 70-180 mg/dL during Weeks 15-16 of the study. The calculations were based on a superiority hypothesis using a t-test at a 2-sided 5% significance level and assumes an absolute difference of at least 4% of time in range, a common standard deviation of 14% (assumed based on the prior AM data from the PDY12777 study), and an expected value of 53% in the Lantus arm. As a generalized linear model with identity link will be used for the primary analysis, the power should be somewhat higher due to reduced estimate variability versus the t-test.

Considering prior data from the AM arms of the PDY12777 and EDITION-4 studies, this sample size would also provide at least 80% power to demonstrate a difference in the key secondary endpoint of the rate of documented symptomatic nocturnal hypoglycemia occurring at any point post randomization, assuming a rate ratio (Toujeo over Lantus) of at most 0.86 events per pt-year. Testing of this key secondary endpoint will be considered informative if superiority of the primary endpoint is met.

With the assumption of approximately 15% drop out rate, approximately 308 patients per treatment arm will provide at least 262 evaluable patients per treatment arm for the study.

Calculations were made using nQuery Advisor v6.01.

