2.3.1 Efficacy populations

2.3.1.1 Modified Intent-to-treat/Modified intent-to-treat population (mITT)

The efficacy analysis population will be the mITT population, which will consist of all patients who are randomized and who have a post-baseline CGM assessment and enough data to calculate the primary endpoint, percent of time in range of 70-180mg/dL (3.9–10mmol/L) during Week 16. Patients will be analyzed as-randomized.

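### SAP 2.4.4.3 tests incidence of nocturnal hypoglycemia ahead of its rate, so the stated 80% power is not the chance of a confirmatory claim on the rate

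*SAP*

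**What the plan says.** SAP 1.3, and Protocol 11.1 in the same terms, single out the rate of documented symptomatic nocturnal hypoglycemia: "this sample size would also provide at least 80% power to demonstrate a difference in the key secondary endpoint of the rate". The assumption is a Toujeo-to-Lantus rate ratio of 0.86 or lower with 262 evaluable patients per arm. The only condition attached is the primary endpoint: "Testing of this key secondary endpoint will be considered informative if superiority of the primary endpoint is met".

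SAP 2.4.4.3 sets the order of testing. The primary endpoint "will be tested first, followed by (1) incidence of nocturnal symptomatic hypoglycemia, (2) rate of nocturnal symptomatic hypoglycemia". Five further tests follow: two on the last four hours of CGM and three on CV%. Each is at the 5% level, and "Inferential conclusions about these successive efficacy endpoints will require statistical significance of the previous one".

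For the incidence step the SAP gives a method only (2.4.4.2): "The incidence (proportion of patients with any nocturnal symptomatic hypoglycemia events) will be analyzed using logistic regression". Protocol 9.2 lists incidence and rate in one bullet. Protocol 11.4.2.3 says that the secondary analyses "will be examined in a hierarchical step-down manner", without giving an order. The numbered order is therefore set in the SAP, and SAP 1.6 does not list it among its modifications.

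SAP 2.3.1.1 limits the efficacy set to patients "who are randomized and who have a post-baseline CGM assessment and enough data to calculate the primary endpoint", so 262 per arm is the relevant number for these tests.

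**The concern.** The two parts of the SAP attach different conditions to the same claim. Under 1.3 the rate can be interpreted once the primary succeeds. Under 2.4.4.3 it also needs a significant difference in the share of patients with any event. The chance of a formal rate claim cannot exceed the power of that incidence test, which is nowhere stated.

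A modest proportional fall in event rate need not change the any-event share by much. If most patients have at least one event in 16 weeks, a 14% fall in the rate leaves most of them with at least one. The trial could then show the planned rate reduction and still be barred from claiming it. The same miss would close the formal route to the last-four-hours and CV% endpoints, which carry the other two secondary objectives in SAP 1.2.2.

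**Working it through.** **Inputs from the documents.** 262 evaluable per arm, 1:1 allocation, rate ratio 0.86, at least 80% rate power (SAP 1.3). The test level is two-sided 5% ("using a t-test at a 2-sided 5% significance level" in 1.3; 5% per step in 2.4.4.3). Treatment lasts 16 weeks, T = 112/365.25 = 0.307 year. The model for the rate is over-dispersed Poisson (SAP 2.4.4.2).

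**Not in the documents.** The Lantus event rate, the over-dispersion, the expected incidence, and how the effect is spread across patients. Everything below is conditional on assumptions about these and on a met primary.

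**The plan's own figures.** For the primary, a difference of 4 with SD 14 and 262 per arm gives 90.5% power (90.4% with the t distribution), as stated. Also 308 × 0.85 = 261.8, consistent with 262. The 80% for the rate can be neither reproduced nor refuted without a Lantus rate and a dispersion, so I solved for the Lantus rate that would make it true.

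**Rate test.** Let μ be the expected events per Lantus patient over 16 weeks and k the between-patient (gamma) frailty variance. Then Var(log RR) = [(1 + 1/0.86)/μ + 2k]/262. For 80% power the bracket must equal 262 × (ln 0.86)²/(1.960 + 0.842)² = 0.759.
- k = 0: μ = 2.163/0.759 = 2.85, or 9.3 events per patient-year.
- k = 0.1: 12.6 per patient-year. k = 0.2: 19.6.
- k of 0.38 or more (0.759/2): no Lantus rate gives 80%.

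**Incidence test, common ratio.** The share with any event is 1 − exp(−μ), or 1 − (1 + kμ)^(−1/k) with frailty. At μ = 2.848 the Lantus share is 94.2%. At 0.86 × 2.848 = 2.450 the Toujeo share is 91.4%. The log-odds difference is 0.429 with standard error 0.344, so power is about Φ(0.429/0.344 − 1.960) = 24%.

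Maximised over every possible Lantus rate, incidence power is 28% at 262 per arm, reached near 5.5 events per patient-year (about 82% against 77% of patients). With 308 per arm the maximum is 32%. Frailty lowers the 262-per-arm maximum to 25%, 23%, 18% and 14% for k = 0.1, 0.2, 0.5 and 1.

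**Both steps, by simulation.** 20,000 trials per case, 262 per arm, Pearson-scaled Poisson for the rate and logistic regression for incidence, no covariates. Ranges are Wald to likelihood ratio. In the event-free cases a share f of Toujeo patients has no events and the rest have mean 2.848 × 0.86/(1 − f), so the overall ratio stays at 0.86. The Lantus rate is 9.3 per patient-year and k = 0.

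| Toujeo effect | Incidence test | Rate test | Both pass |
|---|---|---|---|
| Common ratio | 23-25% | 80% | 22-23% |
| f = 2% | 43-45% | 79% | 39-40% |
| f = 4% | 65-66% | 78% | 56-57% |
| f = 6% | 81-82% | 77% | 67-68% |
| f = 14% (whole effect) | 99.7% | 72% | 72% |

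With a common ratio and the Lantus rate raised to keep 80% rate power, both pass in 14-16% of trials at k = 0.1 and 6-11% at k = 0.2.

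**The case against.** **The 80% is ordinary single-test power.** SAP 1.3 does not present it as the chance of passing the sequence, and the condition on the primary can be read together with the step-down in the multiplicity section. As a reading of the sentence that is fair. It still leaves the reader with a power and a condition for the key secondary endpoint that are not those of the procedure to be run.

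**The order follows the protocol's listing.** Incidence is named before rate in Protocol 5.2 and 9.2, and ranking is the sponsor's choice. That is so. But the sample-size section singles out the rate, and if incidence is to come first its assumption and power belong there.

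**The ratio is stated as an upper limit.** With a common ratio and no frailty, maximum incidence power at 262 per arm rises to 53% at 0.80, 74% at 0.75 and 90% at 0.70. So the 28% cap is specific to 0.86. However, 0.86 is the value to which the 80% is attached.

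**The size rests on unseen inputs.** This stands. The Lantus rates were solved for, not sourced, and the chance that both steps pass runs from 6% to 72% across the cases shown. Covariate adjustment, which the SAP plans, would shift the figures somewhat. None of this supplies the missing incidence assumption.

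**The consequence is limited.** A failed first step removes the formal claim, not the analysis: the rate will still be estimated and reported.

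**Conclusion.** The concern holds. The condition in SAP 1.3 and Protocol 11.1 does not match the sequence in SAP 2.4.4.3, and the stated 80% is the power of the rate test alone. This much follows from the documents without outside figures.

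The size depends on how the effect is spread across patients. Under a common ratio of 0.86 the incidence step fails in most trials in which the planned effect is real. If the effect comes largely from patients who become event-free, the loss is small. No case examined reaches 80% for both steps. Where the rate test itself has 80% power, none could, because the joint chance cannot exceed either test's power.

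The issue is power and the conditions for a claim. The fixed sequence controls type I error in either order.

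**What to change.** In SAP 2.4.4.3, make the rate step (1) and move incidence to the end of the sequence. Placing incidence directly behind the rate would also free the rate, but incidence would then still stand ahead of the last-four-hours and CV% tests.

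If the present order is kept:
1. Restate the 80% in SAP 1.3 and Protocol 11.1 as the power of the rate test alone.
2. Add the power of the sequence, with the assumed Lantus rate, over-dispersion and incidence effect.
3. Align the sentence that makes the rate conditional on the primary with the rule in 2.4.4.3.

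**Cost.** Reordering is a one-line SAP change with no extra patients or data and the same type I error control. Because the trial is open-label, it should be made before database lock and without sight of hypoglycemia results by arm. Changing Protocol 11.1 would go through the amendment process in Protocol 15.

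Incidence loses some chance of a formal claim. Directly behind the rate it falls from about 23% to 22% under a common ratio, or from about 81% to 67% if 6% become event-free. At the end it also depends on the five intervening tests, for which the documents give no power. The rate would in turn stand ahead of those tests, which is a further reason to state its Lantus rate and dispersion.
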